- Significant weight change (10% change in body weight in Kg) from the time of the OSA diagnosis until the study initiation.
- Persistent excessive daytime sleepiness (Epworth Sleepiness scale > 10), despite treatment of OSA
- Significant medical comorbidities requiring restricted oral fluid intake – **decompensated** heart failure, end stage renal disease, end stage liver disease, hyponatremia (**S. Na <130 mg/dl**), nocturia > times/night.
- Significant mental health comorbidities including history of psychogenic polydipsia, obsessive-compulsive behavior, **current** suicidal ideation and uncontrolled anxiety.
- Unable or unwilling to participate in study procedures.
- Previous upper airway surgeries significantly modifying upper airway anatomy.
- Known congenital or acquired diseases significantly affecting upper airway anatomy.
- BMI >40 kg/m².
- Currently treating OSA with hypoglossal nerve stimulator.

Significance: There is a clear unmet need to provide alternative, first-line solutions for both obstructive sleep apnea (OSA) and primary snoring. Most people suffering from OSA are currently not receiving treatment, with estimates of 80% undiagnosed (23 million Americans) and 40% non-adherence to the gold standard treatment, continuous positive air pressure (CPAP), among those diagnosed. This has serious implications for overall health resulting in increased daytime sleepiness and comorbidities of hypertension, heart disease, diabetes, and depression. The undiagnosed population alone contributes to an estimated cost burden of \$30 billion from comorbidities and mental health, \$26.2 billion from motor vehicle accidents, \$6.5 billion from workplace

accidents, and \$86.9 billion from lost productivity, with a total cost burden to the US of \$149.6 billion each year [1]. The aging population in addition to increases in obesity will only make this problem worse [6]. Although most people are undiagnosed, indicators such as snoring can be found in up to 94% of OSA patients [2] and habitual snorers (snoring \geq 3 nights/week) with bed partners often seek treatment for their snoring. Low risk, low burden, and affordable solutions that are easily administered to OSA and primary snoring sufferers open new treatment paradigms to reduce the overall harm from these conditions.

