Following this, the participants will conduct the home sleep apnea test using the provided WatchPAT™ ONE device for baseline measurements of pAHI (PAT Apnea Hypopnea Index), pRDI (PAT Respiratory Disturbance Index), SpO2 measures – ODI (Oxygen Desaturation Index), nadirSpO2 and T90 (Total sleep time < 90% SpO2), and snoring (intensity and percentage of night with snoring). If the subject has completed a WatchPAT clinically at Mayo Clinic within the last 3 months, the baseline WatchPAT is not required to be sent to the participant as the clinical data is accessible and will still be valid.

The measurements of the myofunctional assessment score, home sleep apnea test and questionnaires will be repeated at day 60 (\pm 5 days) after enrollment. Participants will have 15 days to complete the questionnaires after the 60 day visit.

To wash-off the remnant effects of the standard of care (SOC) OSA treatment on their upper airway, participants who are actively using CPAP, mandibular advancement device, or sleep positioning device, would be asked to discontinue the SOC treatment use for 3 nights prior to the baseline and end-of-study testing. The participants will be enrolled in the study on a rolling basis and the study coordinator will hand out randomized kits containing either MT nozzle (intervention group) or the placebo nozzle (control group), 20 participants each, as described above. The participants, PI and SLP will remain blinded to the group assignments. The study coordinator will be unblinded to group assignments. The placebo nozzle will be made out of the same silicone material and resemble the MT nozzle in appearance but will not have the resistance component to provide myofunctional exercises. The smart water bottle with Bluetooth connectivity (Hidrate Spark™) will automatically log each participant's daily fluid intake through the provided nozzle via a compatible smartphone application and share the fluid intake data with the study personnel. All participants will be suggested an intake of approximately 1.2 liters of water per day using the provided water bottle (equivalent of drinking two 20 Oz water bottles). At the

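### The sodium cut-off in the hyponatremia exclusion is printed in mg/dl, a unit that does not fit its number (130) or its label.

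*Protocol*

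**What the plan says.** Under Exclusion Criteria, one bullet of the protocol concerns people who should not drink freely. It opens with "Significant medical comorbidities requiring restricted oral fluid intake" and then names decompensated heart failure, "end stage renal disease, end stage liver disease, hyponatremia" and nocturia. Directly after hyponatremia, a bracket gives a serum sodium limit: below 130, in mg/dl. The limit appears nowhere else in the protocol, so no other place restates it in a different unit.

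The bullet bears on how the study is run. Under Aim 2, the feasibility study in human subjects, the protocol states: "All participants will be suggested an intake of approximately 1.2 liters of water per day using the provided water bottle". This applies in both the therapy-nozzle and the placebo-nozzle arm, with repeat measurements at day 60.

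**The concern.** A laboratory threshold in an eligibility rule has three parts that must agree: the number, the unit, and the condition it is meant to identify. Here they do not. In mg/dl, 130 is a far lower sodium than the same number in mmol/L, and it does not mark off the condition named beside it.

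What is at stake is whether the item works as written. It belongs to the bullet meant to keep out people who need to limit fluids, in a trial where every participant is encouraged to drink a set amount of water. The procedures described under Aim 2 (questionnaires, speech-language examination, home sleep test) include no blood test, and enrolment may be virtual. On that description, the item depends on staff comparing whatever sodium result they have with the written limit. Someone applying the printed unit and someone applying the label could reach opposite decisions about the same patient.

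**Working it through.** **Inputs**

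- Cut-off: serum sodium below 130 mg/dl (Protocol, Exclusion Criteria).
- Molar mass of sodium, M = 22.99 g/mol. This physical constant is not given in the protocol and is taken here as an assumption; the sensitivity is shown in step 2.

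**Formulas**

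- mmol/L = (mg/dl × 10) / M
- mg/dl = (mmol/L × M) / 10

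**Step 1. The printed limit in mmol/L.** 130 × 10 / 22.99 = 1300 / 22.99 = 56.5 mmol/L.

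**Step 2. Sensitivity to the constant.** With M = 22.9 the result is 56.8 mmol/L, with 23.0 it is 56.5, and with 23.1 it is 56.3. The conclusion does not depend on rounding of the molar mass.

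**Step 3. The same number read in mmol/L.** 130 × 22.99 / 10 = 298.9 mg/dl. The ratio to the printed limit is 298.9 / 130 = 2.30.

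**Step 4. Would any plausible sodium value meet the printed limit?**

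| Sodium, mmol/L | Sodium, mg/dl | Below 130 mg/dl? |
|---|---|---|
| 120 | 275.9 | No |
| 125 | 287.4 | No |
| 130 | 298.9 | No |
| 135 | 310.4 | No |
| 140 | 321.9 | No |

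Every value is more than twice the printed limit. Taken literally, the numeric threshold is not met anywhere in this range, including at 120 mmol/L.

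**Step 5. Scope.** The bracket qualifies hyponatremia only. Heart failure, renal disease and liver disease in the same bullet carry no sodium value and exclude patients as before.

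**The case against.** The strongest reply is that this is a slip of labelling that no clinician would act on. The word hyponatremia stands beside the number, and a screener would probably read 130 as mmol/L or mEq/L without noticing the unit. A patient whose low sodium requires fluid restriction would also still fit the bullet's opening phrase, whatever the bracket says. The water intake is a suggestion, made equally in both arms and not stated to be on top of usual intake. What the trial tests is the nozzle, in a study described as non-significant risk. No endpoint, sample size, randomization or analysis is touched.

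Most of this stands, and it limits the point. A reader might infer three stronger things that the document does not support:

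- *That the whole fluid-intake exclusion is void.* It is not; one item's number is affected.
- *That patients with low sodium were or would be enrolled, with this item excluding 0% in practice.* That holds only if staff apply the printed unit and disregard the label. The protocol gives no evidence of this, and no eligibility form or screening log is available.
- *That participants must be re-screened.* Nothing in the document shows that the mg/dl limit was ever applied.

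What the reply does not remove is the contradiction itself. Number, unit and label are all legible, the unit is not corrected elsewhere, and an operative eligibility limit should not depend on staff silently overriding what is written.

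**Conclusion.** The point holds as a unit error in one eligibility item. The printed cut-off equals about 56.5 mmol/L, is smaller by a factor of 2.3 than the same number read in mmol/L, and conflicts with the condition it is supposed to define. This rests only on the printed text and the molar mass of sodium.

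The practical effect is probably small. That is a judgement about how screeners would read the line, not something the protocol shows. The correction is still worth making, because the limit is operative, related to participant safety, and easy to put right. The document does not establish which value and unit were intended, and this review does not choose between them.

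**What to change.** The sponsor should reconcile the sodium cut-off's number and unit with the label hyponatremia in the exclusion criteria, with the medical lead confirming both the intended value and the intended unit. If an eligibility checklist or electronic form reproduces the limit, check that it carries the reconciled unit.

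The cost is a short text correction in the next amendment and a form check. Design, sample size, endpoints and analysis stay as they are.

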We created an innovative myofunctional therapy nozzle that allows the user to repeatedly perform the tongue suction, tongue press, and swallow exercise movements while also providing targeted resistance to train and improve tongue, soft palate, and pharyngeal muscle strength and endurance (**Figure 2**). Key design features of the nozzle promote proper tongue swallowing position and tongue suction motion and resistance during the preparatory and oral phase of the swallow. The nozzle then provides resistance as the tongue compresses the nozzle against the hard palate through the transition of the oral and pharyngeal phases of the swallow. The device promotes 20-50% more daily swallows by limiting water bolus size for each swallow. The device is designed to deliver daily therapy by simply drinking one or two bottles of water (30oz – 60oz), making it simple to keep track of daily therapy. The nozzle is engineered to utilize natural biomechanical motions of the tongue and prevent improper exercise motions, which makes it easy to use with minimal instruction or attention.

[figure not shown]

Figure 2: Depiction of Tongue Suction (left) and Tongue Press (right) Motions.

Our technology has created an oropharyngeal exercise device that has low risk and low burden and can be easily administered to reduce primary snoring and obstructive sleep apnea severity. The user-centric design and unique connection of the therapy with a biologically driven action greatly increases the probability of long-term adherence to the therapy regimen. Our solution has the potential to create a new therapy option for physicians to manage their patients' OSA and snoring.

Approach: In this SBIR Phase I project we will characterize, develop, and test a novel myofunctional therapy nozzle that can be used with a commercially available reusable water bottle and conduct a feasibility study comparing the device vs. a normal water bottle nozzle control to assess adherence and quality of life (QOL) for mild to moderate obstructive sleep apnea patients after two months of device use. Secondary outcome measures will compare changes in myofunctional assessment, AHI, oxygen saturation (SpO₂), and snoring intensity/percentage. Successful outcomes of this Phase I project will be a myofunctional therapy nozzle with characterized key therapy related design variables that has shown feasibility and improved adherence.

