1.a) Build Nozzle with Consistent Radial Compression Force: The therapy compression force requirement range of our nozzle was based on numerous dysphagia studies in the literature that utilized the Iowa Oral Performance Instrument (IOPI), in combination with qualitative testing. The IOPI is a commonly used tool to assess tongue strength and endurance by compressing a bulb against the hard palate with the user's posterior or anterior tongue. We will correlate compression force to IOPI pressure measurements by compressing an IOPIbulb with a force load cell and test stand. The force compression range will be 0 – 100kPa measured by the IOPI[15]. The max compression distance of 100 kPa will be determined by measuring the distance from touching without compression and compressing until the IOPI reads 100kPa. 5 – 10 compression distances within the minand max range will be measured by recording the data point on both the IOPI and the compression load cell at each distance. This test will be repeated until the data is sufficient to understand the relationship. The therapy requirement will be adjusted from IOPI pressure to compression force measured by load cell using the correlation equation determined. Nozzle Radial Compression Characterization testing will be conducted by varying silicone stiffness (durometer) and wall thickness associated with the nozzle. The mold design can be easily iterated upon with CAD software and 3D printing to test varying wall thicknesses. Silicone stiffness can be varied by selecting different durometer grades of silicone used. A load cell and motorized test stand will be used to radially compress the nozzle at a set speed, to mimic the normal speed of swallowing [16,17]. The force data will be analyzed to determine the max radial compression force before the inflection point where the silicone inner walls are touching, and the silicone material is being compressed.

Metric of Success: 30 nozzles will be manufactured within +/- 10kPa (IOPI measurement that will be correlated to radial compressive force) of the desired radial compression force requirement as measured by radial compression testing.

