Aim 2. Conduct feasibility study in human subjects: The goal of Aim 2 is to conduct a feasibility study of the MT nozzle water bottle vs. a normal nozzle (placebo) water bottle in mild and moderate OSA patients. [name] and [name], sleep medicine experts at the Mayo Clinic, will oversee the study. An experienced speech language pathologist (SLP), will perform myofunctional assessment at study entry and after approximately two months of device use to determine if the device is delivering the desired oropharyngeal exercises. 43 participants will be recruited from Mayo Clinic Sleep Disorders Center in Rochester, MN who underwent polysomnography (PSG) or home sleep apnea test (HSAT) within last 2 years and are diagnosed with mild to moderate obstructive sleep apnea (AHI 5-29/hour). Potential participants will be contacted by a member of the Pulmonary Clinical Research Unit (PCRU) to gauge interest in the study. Those interested in participating will be asked to come to Mayo Clinic for enrollment or may enroll via a virtual visit and sign a consent form electronically. REMastered Sleep will provide randomized kits to the PCRU for each enrolled participant containing a clinically validated disposable home sleep apnea test (WatchPAT™ ONE), a smart water bottle with Bluetooth connectivity (Hidrate Spark™), and either an MT nozzle or a placebo nozzle with an instruction sheet on how to use and clean the water bottle and the provided nozzle. Each person who enrolls at Mayo Clinic will receive a kit during the visit. Those enrolled virtually will have kits shipped to their homes. Study IDs will be assigned by the study team at Mayo Clinic.

Prior to the first visit with SLP, each participant will complete a QOL questionnaire such as SAQLI (Sleep Apnea Quality of Life Index). If the participant has a significant other, the significant other will be asked to complete a bed partner survey. Participants will receive these surveys through their email or they may be distributed via paper at the first SLP visit. These surveys will be reviewed by the study coordinator or the PI within 48 hours of completion. The participant will undergo baseline myofunctional measurements conducted with SLP. The myofunctional assessment test includes upper airway and oral exam to calculate a myofunctional assessment score and assess tongue strength and tongue endurance using the Iowa Oral Performance Instrument (IOPI).

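### The exclusions cover upper airway anatomy but not known swallowing or neuromuscular disorders, although the nozzle loads the swallow: a low-severity, precautionary safety gap

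*Protocol*

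**What the plan says.** Two bullets in the Protocol's Exclusion Criteria concern the upper airway, and both are limited to structure: "Previous upper airway surgeries significantly modifying upper airway anatomy" and "Known congenital or acquired diseases significantly affecting upper airway anatomy". The other bullets cover weight change, sleepiness, illness requiring fluid restriction, mental health, BMI and hypoglossal nerve stimulation. There is also one general bullet: "Unable or unwilling to participate in study procedures". No inclusion or exclusion criterion mentions dysphagia, aspiration, or neurological or neuromuscular disease of the tongue, palate or pharynx.

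The device description at the end of the Significance section says what the nozzle does: "The nozzle then provides resistance as the tongue compresses the nozzle against the hard palate through the transition of the oral and pharyngeal phases". It adds: "The device promotes 20-50% more daily swallows by limiting water bolus size for each swallow". Aim 2 suggests about 1.2 L of water per day through the bottle for every participant, for about two months at home.

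Aim 1.a says the compression-force range was "based on numerous dysphagia studies in the literature that utilized the Iowa Oral Performance Instrument (IOPI"). Under Aim 2, the speech-language pathologist's baseline visit produces a myofunctional score and tongue strength and endurance readings. No eligibility consequence is attached to it. Kits are randomized. On-site enrollees receive theirs at the enrollment visit, and for the rest, "Those enrolled virtually will have kits shipped to their homes".

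**The concern.** The criteria screen structure, while the intervention acts on function. The list is otherwise fitted to this device: it removes people for whom extra water is a problem, people prone to compulsive drinking, and users of a nerve stimulator acting on the tongue. Against that background, silence on swallowing disorders looks like an oversight. The only choking hazard the Protocol discusses is a detached nozzle (Aim 1.d).

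What is at stake is mainly precaution. A person with a known, milder swallowing or neuromuscular disorder could be randomized to repeated resisted swallows at home without anyone having been asked to consider whether that is suitable. A smaller issue is that such a person may drink less through the nozzle, or score differently on the tongue measures, for reasons unrelated to the device. Eligibility belongs in the protocol, so an unseen statistical analysis plan would not close this gap.

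**Working it through.** The Protocol gives no figure on this point to reproduce. The check is a reading of the criteria, followed by arithmetic on how much such participants could matter.

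**Who remains eligible.** Take an adult with AHI 5-29, a smartphone, and known mild dysphagia without an anatomical lesion.
- Both airway bullets: not met, because anatomy is unaffected.
- Fluid-restriction, mental health, BMI, sleepiness, weight-change and stimulator bullets: not met.
- General bullet on study procedures: met only if the person cannot do what the study asks, in particular drink through the bottle. Someone who can drink, attend and consent passes.

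**Exposure.** Aim 1.c puts nozzle use below 200,000 cycles a year. That is an upper bound for a wear test, not a count of swallows. 200,000/365 = 548 per day, and 548 × 60 = about 32,900 over 60 days, so actual use lies below those values.

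**Chance of enrolling at least one.** The documents give no prevalence p; the values below are assumptions. Aim 2 allots 20 participants to each arm, so n = 40 and the chance is 1 − (1 − p)^40.

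| Assumed p | At least one among 40 |
|---|---|
| 1% | 33% |
| 2% | 55% |
| 5% | 87% |
| 10% | 99% |

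**Between-arm comparisons.** If k affected participants are randomized 20:20, the chance that all fall in one arm is 2·C(20,k)/C(40,k): 49% for k = 2, 23% for k = 3 and 11% for k = 4. Imbalance is therefore plausible, but it has no preferred direction. Suppose one participant lies 3 SD from the rest (an assumption, and an extreme one). The arm mean moves by 3/20 = 0.15 SD. The standard error of a 20-person mean is 1/√20 = 0.22 SD, and that of the difference between arms is √(2/20) = 0.32 SD. The shift is below the first and about half the second.

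**Within-arm adherence.** The Metric of Success under Aim 2 requires adherence above 50% in the therapy group alone, so the control arm offers no protection. If adherence is counted per person, each affected participant who falls short moves it by 1/20 = 5 points. For example, 11 of 20 (55%) meets the criterion and 10 of 20 (50%) does not.

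**The case against.** The best case for leaving the text alone has several parts.

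**The device may be gentle, and nothing shows harm.** The extra swallows come from smaller boluses, not from more water. The force range comes from dysphagia studies, and the reference list includes a review of tongue strength training in adults with and without dysphagia. The study is labelled non-significant risk, is subject to IRB approval and is overseen by sleep specialists. This stands as far as it goes. A reader might infer that the Protocol exposes people to a demonstrated danger, and the documents do not support that. Equally, the dysphagia studies are used to set a force range, not to argue that unsupervised home use of this nozzle is suitable for people with dysphagia. The question is left unaddressed.

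**The general exclusion already covers it.** In part. It lets an investigator exclude someone who cannot drink through the bottle. It prompts nobody to look for a known milder disorder.

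**Outcomes are compared as changes.** This stands for the secondary measures: a stable deficit at baseline largely cancels in a change score. A reader might infer that these participants would bias the results. The calculation does not support that, since between arms they add noise or chance imbalance.

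**Timing.** A reader might infer that virtual enrollees start using the nozzle before the speech-language pathologist sees them. Aim 2 gives no ship date relative to that visit and no instruction to start on receipt. Myofunctional measurement is set at day 0, and the baseline home sleep test, which is in the same kit, follows it. Holding a kit is not the same as using it, so that inference is dropped.

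**Conclusion.** The point holds as a precautionary safety gap of low severity. As written, people with known milder dysphagia or neuromuscular disease affecting the tongue, palate or pharynx are eligible for a device that adds resistance during the swallow, and the Protocol does not say whether that is intended. That harm could follow is an inference, not something the documents show.

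The consequence for inference is minor. Comparisons between arms are not systematically biased, and even an assumed 3 SD outlier moves an arm mean by less than one standard error. Only the within-arm adherence criterion is directly touched, by 5 points per affected participant on a per-person count; the Protocol does not say how adherence is counted. How often such a person would be enrolled is unknown, because every prevalence used above is assumed.

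**What to change.** Extend the existing anatomy bullet so that it also excludes known swallowing disorders, or neuromuscular disease affecting tongue, palate or pharyngeal function. The investigators should set the clinical threshold. Apply it from history or medical records at screening, before a randomized kit is assigned. Aim 2 describes only contact to gauge interest, with no chart review, so the amendment should say where this check takes place.

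The baseline speech-language pathologist's visit is not a ready-made substitute. As described, it is an oral and upper airway exam with tongue strength and endurance testing, not a swallowing evaluation. On-site participants hold a randomized kit from enrollment, so removing someone on the strength of that visit could be a post-randomization exclusion from arms of 20. If the visit is also meant to decide eligibility, it must come before kit assignment. Otherwise participants identified there should stay in the analysis as randomized.

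The cost is a short protocol amendment, one added question or record check at screening, a few more screen failures and a slightly narrower population.

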Aim 2: Conduct feasibility study in human subjects. We will conduct a randomized, non-significant risk (NSR) device study that will assess adherence and quality of life after two months use of the MT nozzle water bottle vs. control for mild-moderate OSA patients. Secondary outcome measures will compare changes in myofunctional assessment, AHI, oxygen saturation (SpO2), and snoring intensity/percentage using a clinically validated and commercially available home sleep apnea test (*WatchPAT™ One*). Myofunctional measurements will be conducted at day 0 and day 60 using an Iowa Oral Performance Instrument and a myofunctional assessment score. Water consumption will be standardized across subjects through fitting of the MT nozzle and standard nozzle on commercially available water bottles that are Bluetooth enabled to measure water consumption (*Hidrate Spark™*). A questionnaire such as SAQLI (Sleep Apnea Quality of Life Index) will be used to measure QOL. Participants' significant others will be asked to complete a bed partner survey as applicable.

Milestone: Conduct NSR device feasibility study with MT water bottle vs control that assesses adherence to therapy and quality of life after two months of use in mild to moderate OSA patients. Additionally, collect information on changes in snoring, OSA and myofunctional measures.

Our proposed nozzle is a novel, low risk, low burden, and low cost myofunctional device that will be clinically tested for feasibility with mild to moderate OSA patients. A future Phase II project would focus on further therapy optimization and conducting a larger more inclusive clinical trial with emphasis on efficacy. This proposed work has the potential to create a new therapy platform for patients to easily improve their OSA and snoring.

Inclusion Criteria:

- Diagnosis of mild to moderate obstructive sleep apnea with Apnea Hypopnea Index 5-29 events/hour confirmed within last 2 years with an in-lab diagnostic polysomnography or home sleep apnea test.
- Ownership of a smartphone and willingness to use a smartphone application to automatic log daily water intake.
- Willingness and ability to discontinue the currently prescribed OSA treatment for at least 3 days prior to testing.
- Age greater than or equal to 18 years.
- Participants willing to travel to the Rochester area for the Speech and Language Pathologist exam

Exclusion Criteria:

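### The assigned nozzle is issued at enrolment, before the SLP baseline for at least the virtual enrollees and before the study WatchPAT baseline, with no instruction to leave it unused

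*Protocol*

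**What the plan says.** The section on Aim 2 (Conduct feasibility study in human subjects) states that "REMastered Sleep will provide randomized kits to the PCRU for each enrolled participant". Each kit holds the WatchPAT, the smart bottle and either the MT or the placebo nozzle, with a sheet on its use. For on-site enrolment, "Each person who enrolls at Mayo Clinic will receive a kit during the visit". For virtual enrolment, "Those enrolled virtually will have kits shipped to their homes".

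The same section then sets out the baseline measures:

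- **Quality of life.** "Prior to the first visit with SLP, each participant will complete a QOL questionnaire such as SAQLI (Sleep Apnea Quality of Life Index"). On the route, "Participants will receive these surveys through their email or they may be distributed via paper at the first SLP visit".
- **Myofunctional score and IOPI.** "The participant will undergo baseline myofunctional measurements conducted with SLP". The Inclusion Criteria require "Participants willing to travel to the Rochester area for the Speech and Language Pathologist exam".
- **Sleep.** After the SLP assessment, "the participants will conduct the home sleep apnea test using the provided" WatchPAT device. A clinical WatchPAT done at the centre in the last 3 months may stand in for it.

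The repeat measures fall at day 60 (plus or minus 5 days), counted from enrolment. The placebo nozzle looks like the MT nozzle but lacks its resistance. Participants, the PI and the SLP are blinded, and the coordinator is not. I found no instruction to keep the nozzle unused until baseline is complete.

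**The concern.** A baseline should be taken before allocation or, failing that, before the allocated treatment can be used. Here the kit fixes the allocation and puts the nozzle in the participant's hands while some baseline measures are still to come. Two things follow.

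First, a person who enrols and then does not attend the SLP visit, for instance because of the travel, counts as a randomized participant with an incomplete baseline. If nozzles were issued after baseline, the same person would simply not have been randomized.

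Second, a person who stays can start using the nozzle before tongue strength or the sleep indices are measured. That baseline is then a post-treatment value, and change from it understates whatever effect has already appeared.

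The myofunctional measures carry weight in this plan. The Alternatives paragraph of Aim 2 turns to them if quality of life shows no significant difference, and they are the one set of baseline values that every early leaver lacks.

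**Working it through.** The protocol states no figure on this point, so the check is one of sequence, followed by a bound on the numbers.

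**Order of events, from the Aim 2 section**

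| Step | On-site enrollee | Virtual enrollee |
|---|---|---|
| Allocated nozzle in hand | At the enrolment visit | By mail after enrolment |
| SAQLI, partner survey | By email before the SLP visit, or on paper at it | Same |
| SLP exam and IOPI | Possibly the same day; order relative to the kit not stated | Later, in Rochester; it cannot be done at a virtual visit |
| Baseline WatchPAT | At home after the SLP exam, unless a recent clinical test is used | Same |

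The nozzle therefore precedes the SLP baseline for virtual enrollees. It precedes the study WatchPAT for both groups, because that device comes in the same kit and is used after the exam.

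**What an early leaver has on record.** For someone who drops out after receiving the kit and before the SLP visit:

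- Myofunctional score and IOPI: never.
- SAQLI: yes if completed by email; no if it was to be done on paper at the visit.
- Sleep measures: only if a clinical WatchPAT from the last 3 months exists.

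**Effect of use before baseline.** Let E60 be the MT-minus-placebo effect at the end of study, and Eb the effect already present when baseline is measured. The between-group difference in change is then E60 − Eb. Eb is zero for a clinical WatchPAT that predates enrolment and for a SAQLI completed before first use. It need not be zero for IOPI in virtual enrollees or for the study WatchPAT. The document gives nothing from which to size Eb.

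**Number of early leavers.** Inputs are 43 to be recruited and 20 per group (both Aim 2). The margin is 43 − 2 × 20 = 3, or 3/43 = 7.0%; the protocol does not call it a dropout allowance. Let v be the share of enrollees with a gap between kit and SLP visit, and w the loss rate in that gap. The expected number is 43 × v × w. The protocol gives neither v nor w. With w *assumed* at 5% to 15%:

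- v = 1 (upper bound): 43 × 0.05 = 2.15 to 43 × 0.15 = 6.45.
- v = 0: none.

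For scale, the probability that at least 40 of 43 remain under an *assumed* independent loss rate from any cause is the binomial tail P(X ≥ 40), with X ~ Bin(43, 1 − rate):

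| Assumed loss | Expected remaining | P(at least 40) |
|---|---|---|
| 5% | 40.9 | 0.83 |
| 10% | 38.7 | 0.36 |
| 15% | 36.6 | 0.10 |

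A margin of 3 absorbs few losses, so avoidable post-randomization losses are worth removing. These rates illustrate and do not forecast.

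**The case against.** The best defence is that the gap may be small. The protocol elsewhere places the SLP assessment at entry to the study and the myofunctional measures at day 0, and it counts day 60 from enrolment. For on-site enrollees the kit and the exam may fall on the same day, so the SLP gap may be nil. This stands for on-site enrollees. It does not close the gap for virtual enrollees, or for the study WatchPAT, which is taken at home after the exam in both groups.

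A reader might infer that the kit precedes every baseline measure, so that every early leaver has none. The text does not support that. SAQLI, which the protocol names as its example of the quality-of-life questionnaire, is due before the SLP visit and may come by email. A recent clinical WatchPAT can supply the sleep baseline.

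A reader might also infer that early leavers left because of the nozzle, and that later issue would remove this bias. Only the MT nozzle has resistance, so arm-dependent dropout is possible despite blinding, but nothing in the document shows it. People who quit because of the nozzle cannot quit before they have it; with later issue they would still be lost after randomization. People who leave for reasons unrelated to a blinded allocation, such as travel, cost precision rather than introduce bias. In either case an early leaver has no day-60 value and so no change score.

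Two further points stand. Adherence, one of the two success metrics, needs no baseline. How incomplete baselines are analysed may be settled in a statistical section not shown here. That section could not, however, undo an order of issue that the protocol fixes.

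**Conclusion.** The point holds in limited form. Allocation and possible use of the nozzle come before the SLP baseline for at least the virtual enrollees, and before the study WatchPAT for everyone who needs one. Early leavers are randomized losses with an incomplete baseline, and some of those who stay may have a baseline measured after use began.

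The size cannot be fixed from the document. The count of early leavers ranges from none to about 6 of 43. The upper end assumes that every enrollee has a gap and that 15% are lost in it. The effect of early use on the change scores is not quantified.

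Later issue would gain three things. Those who leave before the SLP visit would not be randomized. Those who leave after trying the nozzle would have a full baseline on record. No baseline would be measured after use. It would not prevent dropout caused by the nozzle. The change is worth making because it is cheap, the sample is small, and neither problem can be repaired after the data are collected.

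**What to change.** Split the kit and tie nozzle issue to the end of baseline:

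1. At enrolment, hand over or ship only the unallocated parts: the WatchPAT where one is needed, and the survey link.
2. Have SAQLI and, where needed, the baseline WatchPAT completed before the SLP visit.
3. At that visit, after the exam, have the unblinded coordinator allocate and issue a sealed, numbered nozzle pack. The SLP should not handle it, so that the SLP's blinding is kept.
4. If the WatchPAT must stay after the SLP visit, state that the nozzle is not used until the test is complete. Moving nozzle issue alone would leave the sleep baseline exposed.
5. State whether day 60 runs from enrolment or from nozzle issue. With later issue, a clock started at enrolment would shorten the period of use.

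The cost is packing each kit in two parts, a few protocol sentences, and the coordinator's presence for the hand-over. The nozzle could no longer be mailed at enrolment. No visit is added, since the SLP exam already requires attendance in person.
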